6.1 Involvement of minors. Does your research include minors (children)?

Minor or child means someone who has not yet attained the legal age for consent for the research procedures, as described in the applicable laws of the jurisdiction in which the research will be conducted. This may or may not be the same as the definition used by funding agencies such as the National Institutes of Health.

- In Washington State the generic age of consent is 18, meaning that anyone under the age of 18 is considered a child.
- There are some procedures for which the age of consent is much lower in Washington State. See the WORKSHEET: Children for details.
- The generic age of consent may be different in other states, and in other countries.

 No	→ If no, go to Section 8 .
 Yes	→ If yes, provide the age range of the minor subjects for this study and the legal age for consent in your population(s). If there is more than one answer, explain.

N/A

 Don't know	→ This means is it not possible to know the age of your subjects. For example, this may be true for some research involving social media, the Internet, or a dataset that you obtain from another researcher or from a government agency. Go to Section 8 .
--	--

7.5 Children who reach the legal age of consent during participation in longitudinal research.

Children who were enrolled at a young age and continue for many years: It is best practice to re-obtain assent (or to obtain it for the first time, if you did not at the beginning of their participation).

Children who reach the legal age of consent: You must obtain informed consent from the now-adult subject for (1) any ongoing interactions or interventions with the subjects, or (2) the continued analysis of specimens or data for which the subject's identify is readily identifiable to the researcher, unless the IRB waives this requirement.

- a. Describe your plans (if any) to re-obtain assent from children.

N/A

- b. Describe your plans (if any) to obtain consent for children who reach the legal age of consent.

- If you plan to obtain consent, describe what you will do about now-adult subjects whom you are unable to contact.
- If you do not plan to obtain consent or think that you will be unable to do so, explain why.

N/A

7.6 Other regulatory requirements. (This is for your information only; no answer or response is required.)

Researchers are responsible for determining whether their research conducted in schools, with student records, or over the Internet comply with permission, consent, and inspection requirements of the following federal regulations:

- PPRA – Protection of Pupil Rights Amendment
- FERPA – Family Education Rights and Privacy Act
- COPPA – Children's Online Privacy Protection Act

8 CONSENT OF ADULTS

Review the following definitions before answering the questions in this section.

CONSENT

is the process of informing potential subjects about the research and asking them whether they want to participate. It usually (but not always) includes an opportunity for subjects to ask questions. It does not necessarily include the signing of a consent form. This question is about the consent process.

CONSENT DOCUMENTATION

refers to how a subject's decision to participate in the research is documented. This is typically obtained by having the subject sign a consent form.

CONSENT FORM

is a document signed by subjects, by which they agree to participate in the research as described in the consent form and in the consent process.

ELEMENTS OF CONSENT

are specific information that is required to be provided to subjects.

PARENTAL PERMISSION

is the parent's active permission for the child to participate in the research. Parental permission is subject to the same requirements as consent, including written documentation of permission and required elements.

SHORT FORM CONSENT is an alternative way of obtaining written documentation of consent that is most commonly used with individuals who are illiterate or whose language is one for which translated consent forms are not available.

WAIVER OF CONSENT means there is IRB approval for not obtaining consent or for not including some of the elements of consent in the consent process.

WAIVER OF DOCUMENTATION OF CONSENT means that there is IRB approval for not obtaining written documentation of consent.

8.1 Groups Identify the groups to which your answers in this section apply.

Adult subjects

Parents who are providing permission for their children to participate in research

→ If you selected **PARENTS**, the word "consent" below should also be interpreted as applying to parental permission and "subjects" should also be interpreted as applying to the parents.

8.2 The consent process. This series of questions is about whether you will obtain consent for all procedures except recruiting and screening and, if yes, how.

The issue of consent for recruiting and screening activities is addressed in [question 4.6](#). You do not need to repeat your answer to question 4.6.

a. Are there any procedures for which you will not obtain consent?

No

Yes → If yes, use the table below to identify the procedures for which you will not obtain consent. "All" is an acceptable answer for some studies.

Be sure to consider all research procedures and plans, including future contact, and sharing/banking of data and specimens for future work.

Group ¹	Describe the procedures or data/specimen collection (if any) for which there will be NO consent process	Reason why you will not obtain consent	Will you provide subjects with info about the research after they finish?	
			YES	NO
				
				
				
				

Table footnotes

1. If your answer is the same for all groups you can collapse your answer across the groups and/or procedures.

b. Describe the consent process, if you will obtain consent for any or all procedures, for any or all groups. Address groups and procedures separately if the consent processes are different.

Be sure to include:

- The location/setting where consent will be obtained
- Who will obtain consent (refer to positions, roles, or titles, not names).
- Whether/how you will provide an opportunity for questions
- How you will provide an adequate opportunity for the subjects to consider all options

Client Participants

Research staff will describe the study to the clients after their treatment group (or at a different time, if requested by a potential participant). Uninterested clients will then leave. There are three consent forms (a) the main consent, (b) follow-up locating consent form and (c) release of information form for their agency to release the medical record to the study. Research staff will distribute and review the consent forms with all interested clients. Clients will then be directed to review the consent forms individually and ask any questions they have about the study. Potential participants willing to participate will be asked to sign the consent form and then complete Contact Information Form and gift certificate reimbursement information.

Counselor Participants

Research staff will describe the study to the counselors. Uninterested counselors will then leave. Research staff will distribute and review the consent form with all interested counselors. Counselors will then be directed to review the consent form individually and ask any questions they have about the study. Potential participants willing to participate will be asked to sign the consent form, provide an email or phone number to be texted or called for follow-up assessments, and the gift certificate reimbursement information.

If either client or counselor participants do not want their agency to know that they did not want to participate, they will be told they are free to write random words on the consent form and/or questionnaires so no one else will know they were not participating.

Our goal is to attempt recruitment of all counselors at each site at each Step of the study. At Steps 2-6, the study will reach out to the site's point of contact to determine if there are any counselors who have left or new counselors hired since the previous Step. New counselors can then be recruited. To prevent inadvertent re-recruitment of counselors who refused to participate at an earlier Step, we will retain their names only in our records so that the research staff can provide a complete list of counselors from the previous Step to the site point of contact and clarify who refused so they won't be re-recruited.

Follow-up Locating Consent Form to Prevent Client Participant Attrition.

Our goal is for all participants to complete all outcome assessments regardless of treatment participation. Therefore, informed consent will include a separate locating consent form on which client participants choose locating strategies they consent to have used (e.g., obtaining forwarding address from post office, checking social media) and provide alternative contacts to whom the study can reach out in case the participant moves or changes contact information.

This form is separate from the main consent so that if we have to provide to a contact so they know we have permission to get the client's contact information, we are not sharing any information about the study, their drug use, etc. We have used this locating consent form for over 20 years of research. It finds an excellent balance between obtaining detailed information and allowing participants to only provide information they are comfortable providing.

Administrative Supplement

A horizontal bar chart illustrating the percentage of the population aged 15-24 in each state and the District of Columbia. The x-axis represents the percentage, ranging from 0% to 100% in increments of 10%. The y-axis lists the entities: California, Texas, Florida, New York, Illinois, Michigan, Ohio, Pennsylvania, New Jersey, Massachusetts, Connecticut, Rhode Island, New Hampshire, Vermont, New Mexico, Kansas, Missouri, Oklahoma, Louisiana, Mississippi, Alabama, Georgia, North Carolina, South Carolina, Virginia, Maryland, Delaware, District of Columbia, and Alaska. The bars are colored in a gradient from light gray (representing lower percentages) to dark gray (representing higher percentages). The chart shows that the District of Columbia and California have the highest percentages, while Alaska and the District of Columbia have the lowest.

Entity	Percentage (%)
California	88
Texas	87
Florida	86
New York	85
Illinois	84
Michigan	83
Ohio	82
Pennsylvania	81
New Jersey	80
Massachusetts	79
Connecticut	78
Rhode Island	77
New Hampshire	76
Vermont	75
New Mexico	74
Kansas	73
Missouri	72
Oklahoma	71
Louisiana	70
Mississippi	69
Alabama	68
Georgia	67
North Carolina	66
South Carolina	65
Virginia	64
Maryland	63
Delaware	62
District of Columbia	61
Alaska	59

c. Comprehension. Describe how you will ensure or test the subjects' understanding of the information during the consent process.

The main points of the consent form will be reviewed with opportunities to ask question before the participants are asked to review and sign the informed consent form to assure that they understand.

d. Influence. Does your research involve any subject groups that might find it difficult to say “no” to your research because of the setting or their relationship with you, even if you don’t pressure them to participate?

Examples: Student participants being recruited into their teacher's research; patients being recruited into their healthcare provider's research, study team members who are participants; outpatients recruited from an outpatient surgery waiting room just prior to their surgery.

No

Yes

→ If yes, describe what you will do, for each of these subject groups, to reduce any effect of the setting or relationship on their decision.

Examples: a study coordinator will obtain consent instead of the subjects' physician; the researcher will not know which subjects agreed to participate; subjects will have two days to decide after hearing about the study.

All client participants will be asked by their counselors at the end of a standard treatment group in their IOP if they would like to volunteer for a study that involves staying after that group (or participating before or after one of the other IOP groups that week, if that day is not convenient). Client participants will be told by the agency and the study that this study is voluntary and will not affect their treatment nor will any data provided be shared with the agency unless the client reports suicide risk in which case the study will coordinate with the client and agency to assure adequate care. As noted above, if either clients or counselors do not want to participate, they can write nonsense on the forms so others do not know they are declining.

See 8.2b above for how this is addressed for the administrative supplement.

e. Ongoing process. For research that involves multiple or continued interaction with subjects over time, describe the opportunities (if any) you will give subjects to ask questions or to change their minds about participating.

Participants are free to stop participating any time as described in the consent form. If a participant no longer wishes to participate, they can decline when we contact them for follow-up assessments. We will ask them to elaborate on why they would like to discontinue participation in the study as this will help with current and future retention, but they are free to say that it is for no reason or they do not want to give a reason.

8.3 Written documentation of consent. Which of the statements below describe whether you will obtain documentation of consent? NOTE: This question does not apply to screening and recruiting procedures which have already been addressed in [question 4.6](#).

Documentation of consent that is obtained electronically is not considered written consent unless it is obtained by a method that allows verification of the individual's signature. In other words, saying "yes" by email is rarely considered to be written documentation of consent

a. Are you obtaining written documentation of consent for:

 None of your research procedures	→ Use the table below to provide your justification then go to question 8.4 .
 All of your research procedures	→ Do not complete the table; go to question 8.3.b .
 Some of your research procedures	→ Use the table below to identify the procedures for which you will not obtain written documentation of consent from your adult subjects.

Adult subject group ¹	Describe the procedures or data/specimen collection (if any) for which there will be NO documentation of consent	Will you provide them with a written statement describing the research (optional)?	
		YES	NO
Counselor Participants	We have decided that the study Steps will be 4 months in duration instead of 6 months as is currently approved.		
Counselor Participants	We have decided to add a final (7th) assessment for Counselor participants to allow us to determine the impact of Step 6.		
Also see 'Procedure Stage' in Section 5.1			

Stakeholder Participants	As described in 8.2b, there is no reason to increase confidentiality risk for study participants in the Administrative Supplement focus groups and cognitive interviews by de-anonymizing them for the purpose of written consent.				
--------------------------	--	-------------------------------------	--------------------------	--------------------------	--------------------------

Table footnotes

1. If your answer is the same for all adult groups or all procedures, you can collapse your answer across the groups and/or procedures.

8.4 Non-English-speaking or -reading adult subjects. Will you enroll adult subjects who do not speak English or who lack fluency or literacy in English?

	No
	Yes

→ If yes, describe the process you will use to ensure that the oral and written information provided to them during the consent process and throughout the study will be in a language readily understandable to them and (for written materials such as consent forms or questionnaires) at an appropriate reading/comprehension level.

N/A

a. **Interpretation.** Describe how you will provide interpretation and when. Also, describe the qualifications of the interpreter(s) – for example, background, experience, language proficiency in English and in the other language, certification, other credentials, familiarity with the research-related vocabulary in English and the target language.

N/A

b. **Translations.** Describe how you will obtain translations of all study materials (not just consent forms) and how you will ensure that the translations meet the UW IRB's requirement that translated documents will be linguistically accurate, at an appropriate reading level for the participant population, and culturally sensitive for the locale in which they will be used.

N/A

8.5 Barriers to written documentation of consent. There are many possible barriers to obtaining written documentation of consent. Consider, for example, individuals who are functionally illiterate; do not read English well; or have sensory or motor impairments that may impede the ability to read and sign a consent form.

a. Describe your plans (if any) for obtaining written documentation of consent from potential subjects who may have difficulty with the standard documentation process (that is, reading and signing a consent form). Skip this question if you are not obtaining written documentation of consent for any part of your research.

Examples of solutions: Translated consent forms; use of the Short Form consent process; reading the form to the person; excluding individuals who cannot read and understand the consent form.

If a participant is unable to read a consent, due to visual impairment, study staff will read the consent to the participant. We will have the participant sign to the best of their ability, and then print by the research

study team. We will also have a witness sign the consent for added precaution. All of this will be clearly documented within our tracking systems to ensure clarity.

8.6 Deception. Will you deliberately withhold information or provide false information to any of the subjects?

	No
	Yes

→ If yes, describe what information and why.

Example: you may wish to deceive subjects about the purpose of the study.

N/A

a. Will you debrief the subjects later? (Note: this is not required.)

	No
	Yes

→ If yes, describe how you will debrief the subjects. Upload any debriefing materials, including talking points or a script, to the **Consent Form and Recruitment Materials** SmartForm of **Zipline**.

N/A

8.7 Cognitively impaired adults, and other adults unable to consent.

a. **Cognitively impaired adults and other adults unable to consent.** Do you plan to include such individuals in your research?

Examples: individuals with Traumatic Brain Injury (TBI) or dementia; individuals who are unconscious, or who are significantly intoxicated.

	No
	Yes

→ If no, go to [question 8.8](#).

→ If yes, answer the following questions.

a.1. **Rationale.** Provide your rationale for including this population in your research.

N/A

a.2. **Capacity for consent / decision making capacity.** Describe the process you will use to determine whether a cognitively impaired individual is capable of consent decision making with respect to your research protocol and setting. If you will have repeated interactions with the impaired subjects over a time period when cognitive capacity could increase or diminish, also describe how (if at all) you will re-assess decision-making capacity and consent during that time.

N/A

a.3. **Permission (surrogate consent).** If you will include adults who cannot consent for themselves, describe your process for obtaining permission ("surrogate consent") from a legally authorized representative (LAR).

For research conducted in Washington State, see the [SOP: Legally Authorized Representative](#) to learn which individuals meet the state definition of "legally authorized representative".

N/A

a.4. Assent. Describe whether assent will be required of all, some, or none of the subjects. If some, indicate which subjects will be required to assent and which will not (and why not). Describe any process you will use to obtain and document assent from the subjects.

N/A

a.5. Dissent or resistance. Describe how you will identify the subject's objection or resistance to participation (including non-verbal) during the research, and what you will do in response.

N/A

8.8 Consent-related materials. Upload to the **Consent Forms and Recruitment Materials** SmartForm of **Zipline** all consent scripts/talking points, consent forms, debriefing statements, Information Statements, Short Form consent forms, parental permission forms, and any other consent-related materials you will use.

- *Translations must be included.* However, you are strongly encouraged to wait to provide them until you know that the IRB will approve the English versions.
- *Combination forms:* It may be appropriate to combine parental permission with consent, if parents are subjects as well as providing permission for the participation of their children. Similarly, a consent form may be appropriately considered an assent form for older children.
- *For materials that cannot be uploaded:* upload screenshots or written descriptions that are sufficient to enable the IRB to understand the types of data that will be collected and the nature of the experience for the participant. You may also provide URLs (website addresses) or written descriptions below. Examples of materials that usually cannot be uploaded: mobile apps; computer-administered test; licensed and restricted standardized tests.

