All IOP counselors will be trained in the Step where they are randomized to implement PARS. In this way, the study sites are “engaged” in the research as counselors on site will provide the study interventions. The agencies will be deferring human subjects review to the UW and have completed an Institutional Agreement for IRB Review (IAIR) with each site.

[name], who developed PARS, will provide all the training. To maximize the value to our community partners and assure a counselor trained in PARS is available on the day the PARS module is scheduled, all consenting counselors will be offered the opportunity to participate in the training so that someone can substitute if the designated PARS counselor is unavailable.

PARS counselor adherence will be evaluated at the first PARS administration by having an adherence coder sit in on the PARS session. Observation is the method requested by the agency treatment partners as least disruptive and most acceptable to clients. As adherence coders will have participant contact and be hearing the treatment session, they will complete any training on specific agency procedures regarding treatment observers with regard to client PHI so the adherence coders meet all agency standards. No client PHI will be collected as part of adherence coding – the focus is on the counselor’s level of adherence to PARS and not client identity nor comments.

Both Conditions:

Any additional treatments outside of the IOP program (e.g., mental health-oriented counseling, pharmacotherapy) will be available during all phases of the Stepped design. Washington State mandates self-help group attendance in addition to attendance of group and individual IOP sessions; this will also remain consistent throughout each site’s participation (regardless of when PARS is implemented at each site).

Client Participant Assessment Procedures:

Reminder – clinics are randomized at the clinic level. Clients and counselors have no choice in if they receive the intervention. This randomization effects clients and counselors regardless of whether they are study participants or not. As noted above, participants are informed about this in the consent form and we request waiver of consent for the non-participants.

Baseline Assessment

Will always occur one week prior to session intervention.

Will be conducted by in-person group administration. Assessments will be completed on paper or tablet computers. Expected to take 15-30 minutes.

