Participants will be reimbursed (in a choice of gift cards) \$30 for their time for each baseline, \$20 for post-treatment, and follow-up assessments in increments of \$10 for each 10 questions completed. To minimize attrition, participants will also be offered an addition incentive to be paid at the final 6-month assessment (or end of the 6-month assessment window if they do not complete it). The additional incentive (also in gift cards) will be \$20 for completing 2 of the 3 outcome assessments and \$30 for completing all outcome assessments.

C.7. Data Analytic Plan

Data screening and preliminary analyses. First, exploratory data analysis will be performed to characterize the distributional characteristics of all variables. Frequency distributions and plots will be examined to identify out-of-range values and to assess data distributions. To assess scale reliability and validity, item structure will be examined using Cronbach's alpha and factor analysis. Descriptive statistics, stratified by site and study condition, will be examined to characterize sample characteristics and assess randomization. Baseline characteristics including socio-economic status, gender, suicidality, or substance use found to vary significantly between study conditions will be included as covariates in subsequent outcome analyses. Plots of mean outcomes by assessment point, site, and study condition will be examined to characterize outcome trajectories over time and inform the parameterization of time in the longitudinal models. Because differential attrition can compromise inference about experimental effects, we will compare dropouts and completers on demographic characteristics and available outcome variables.

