Primary outcome analyses. In the proposed stepped wedge design, 15 addiction treatment sites that initially provide TAU (Step 1) will be randomized to implement PARS beginning at one of five ensuing steps (Steps 2-6), 3 sites at a time. Participants recruited at each step will be assessed at points: baseline, post-treatment (information and attitudes only), 1, 3, and 6 months. The primary outcome analyses will be intent-to-treat analyses that include all participants, including those with incomplete follow-up data. The primary outcomes will be 1) knowledge about suicide, 2) maladaptive attitudes towards suicide, and 3) help-seeking behaviors. Each outcome will be evaluated in a separate generalized linear mixed model (GLMM)⁶⁰ to evaluate the effect of PARS program vs. Treatment As Usual on change in each outcome over time. The GLMM approach accounts for within-individual and between-group variance and is well-suited for the analyses of multisite, repeated measures data. A logit link function will be used to model dichotomous outcomes and a Gaussian link function when the outcome is relatively normally distributed.

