*The following regression equation depicts the basic model for each outcome: $OUTCOME_{tis} = b_0 + b_1 STEP2_{is} + b_2 STEP3_{is} + b_3 STEP4_{is} + b_4 STEP5_{is} + b_5 STEP6_{is} + b_6 SETTING_{is} + b_7 PARS_{is} + b_8 MONTH1_{tis} + b_9 MONTH3_{tis} + b_{10} MONTH6_{tis} + b_{11} (PARS_{is} * MONTH1_{tis}) + b_{12} (PARS_{is} * MONTH3_{tis}) + b_{13} (PARS_{is} * MONTH6_{tis}) + u_{0s} + r_{0is} + e_{tis}$, where t indexes the assessment, i indexes the individual, and s indexes the site. In this model, each outcome is regressed on Step, Setting (Rural vs. Urban), Treatment (PARS vs. TAU), Time (in months), and the Treatment by Time interaction. The effect of Step will be coded into contrasts of Step 1 against each subsequent step (i.e., Step 2 vs 1, Step 3 vs 1, etc.). The effect of Time will be coded into contrasts of baseline (BL) against each post-baseline assessment (i.e., BL vs. 1 month, BL vs. 3, BL vs. 6 months). To account for the cluster-randomized design, a random effect for site (u_{0s}) will be included to model the correlation of individuals from the same site. To account for the repeated assessments, a random effect for participant (r_{0is}) will be included to model the correlation of observations within the same individual. The statistical test of the treatment effect will be the magnitude and statistical significance of the Treatment by Time interactions. Comparable analyses will be used for exploratory aims with suicidality and substance use.*

Since this study will be carried out at 15 sites, there is the potential for site-specific effects. We anticipate intervention effects to be comparable across all clinics since they are all serving similar client populations and have counselors with comparable levels of experience and training. To verify that treatment effects are comparable across site, preliminary outcome analyses will incorporate indicator variables for site and their interactions with the treatment effects. A likelihood ratio test will be used to compare the models with and without site-specific effects. If the likelihood ratio tests reveal differences in treatment effect by site, these

site-specific parameters will be retained in the final analyses, otherwise they will be excluded.

Secondary Analyses

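### A client can sign the consent, hide a refusal by spoiling only the questionnaire, and still be counted and analysed as a participant

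*Protocol*

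**What the plan says.** **How people may decline.** Protocol 8.2 b first gives an open exit, before any forms are handed out: "Uninterested clients will then leave". For clients or counselors who do not want their agency to know that they declined, it adds that "they will be told they are free to write random words on the consent form and/or questionnaires so no one else will know". Section 8.2 d repeats the offer: "they can write nonsense on the forms so others do not know they are declining".

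**What makes someone a participant.** Section 8.2 b: "Potential participants willing to participate will be asked to sign the consent form and then complete Contact Information Form". The client packet has three forms: the main consent, a locating consent, and a release for the agency's medical record. Section 5.2 says the study obtains that record for each participant.

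**How baseline is collected.** Protocol 5.1: "Will be conducted by in-person group administration. Assessments will be completed on paper or tablet computers". By Protocol 5.13, knowledge items are True/False with an opt-out code, attitude items run from 1 to 5, and help-seeking items are frequency categories.

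**Who is analysed.** SAP C.7: "The primary outcome analyses will be intent-to-treat analyses that include all participants, including those with incomplete follow-up data". Baseline is the reference level: "The effect of Time will be coded into contrasts of baseline (BL) against each post-baseline assessment". The data check is this: "Frequency distributions and plots will be examined to identify out-of-range values and to assess data distributions". Missing data are multiply imputed, with a comparison of results with and without imputation.

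**The concern.** The instruction covers two different acts. Spoiling the consent form leaves no valid consent, so that person should not be enrolled. Spoiling only the questionnaire leaves a signed consent beside answers that mean nothing. The available text does not say who recognises such a record, how it is marked, or that it is removed.

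Two things are at stake. The first is data quality. An invalid baseline would enter the reference level of every time contrast, and the treatment test is the Treatment by Time interaction. If the person later gives no follow-up, imputed values would rest partly on that baseline. The second is consent. Someone the protocol regards as not participating would be counted toward the 900 and analysed. If the release was signed too, their treatment record could be requested. This second harm does not depend on how many people take the route.

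Without a rule set in advance, any later removal of records that look like nonsense would be a judgement made after data are in hand.

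**Working it through.** **1. Follow each route through the plan.**

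| What the decliner does | Consent valid? | Caught by the stated check? | Status under the plan |
|---|---|---|---|
| Leaves before forms are handed out | No | Not needed | Not enrolled |
| Spoils the consent form | No | Not needed | Should not be enrolled; no written rule |
| Signs, writes words on a paper questionnaire | Yes | Visible and not codable | Enrolled, baseline items missing |
| Signs, ticks or taps at random | Yes | No, the values are in range | Enrolled, invalid baseline analysed |

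The last two rows are the gap, and the last is the one that data screening cannot see.

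**2. How many.** The documents give no rate of covert refusal. SAP C.1 reports 79 approached and 78 consenting in the pilot, so open refusal was 1/79 = 1.27%. At the same share, 900 × 1/79 = 11.4 clients. A hidden refusal would itself have been counted as consent, so this is a reference point and not an estimate.

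**3. Reproduce the planned power.** SAP C.7 gives 15.6% against 28.1% at month 1, 15 sites, 6 steps and 10 clients per site per step (15 × 6 × 10 = 900), with power of 89%, or 80% at N = 675. Neither alpha nor the intracluster correlation (ICC) is stated in that paragraph. I assume two-sided 0.05 and use the Hussey and Hughes variance:

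v = I·s²(s² + T·τ²) / [(IU − W)s² + (U² + ITU − TW − IV)τ²]

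- I = 15, T = 6. From the SAP's Figure 1, U = 45, W = 495, V = 165.
- IU − W = 675 − 495 = 180. U² + ITU − TW − IV = 2025 + 4050 − 2970 − 2475 = 630.
- Pooled rate (0.156 + 0.281)/2 = 0.2185, so individual variance = 0.2185 × 0.7815 = 0.1708, and s² = 0.01708 at 10 per cell.
- With ICC 0.003, τ² = 0.003/0.997 × 0.1708 = 0.000514.
- v = 0.00152, standard error 0.0390, and power = Φ(0.125/0.0390 − 1.96) = 89.37%. At 7.5 per cell it is 79.89%.

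ICC 0.003 is simply the value that matches both stated powers. For comparison, ICC 0.05 gives 78.2% and 67.5%.

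**4. Effect of signed covert decliners.** Let q be their share. If they stay in and their outcomes carry no PARS effect, the difference shrinks to 12.5 × (1 − q) points. If they are removed, each cell has 10 × (1 − q) clients. Every q below is an assumption.

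| q | Records of 900 | Difference if kept | Power if kept | Power if removed |
|---|---|---|---|---|
| 1/79 | 11.4 | 12.34 | 88.61% | 89.01% |
| 2% | 18 | 12.25 | 88.15% | 88.80% |
| 5% | 45 | 11.88 | 86.13% | 87.89% |
| 10% | 90 | 11.25 | 82.27% | 86.23% |

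Against 89.37%, keeping these records costs 0.8, 1.2, 3.2 and 7.1 points. This assumes that their answers are unrelated to condition and that the outcome variance is unchanged.

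**The case against.** **The wording speaks of words and nonsense, not plausible ticks.** This is partly right. Literal words on closed paper items would be noticed and would become missing. But baseline may be on a tablet, and the natural way to hide a refusal there is to tap answers. Even the visible case has no written consequence once the consent is signed.

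**The spoiled questionnaire may be meant only as cover for someone who has already spoiled the consent form.** That is a fair reading, and such a person does need something to do in a group setting. The text does not limit itself to that case, however. The fix should keep the cover.

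**Easier exits exist.** Clients can leave, ask for an individual assessment, skip items, or decline at follow-up, and questionnaires have a blank cover sheet. All this stands and is a good reason to expect small numbers.

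**The SAP already looks at missing-data patterns and compares results with and without imputation.** This would show how much imputed follow-up matters. It would not identify or remove an invalid baseline, which is present in both analyses.

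**A reader might infer bias between conditions**, because participants are unblinded and PARS sites discuss suicide. The documents do not support this. Clients are new at each Step (Protocol 1.6) and baseline comes one week before the session (Protocol 5.1), so clients at PARS sites have not had PARS when they decide.

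**Handling of declined forms may be described elsewhere.** Consent pages and some sections are not in the text available here, so the gap is established only for what can be read.

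**Conclusion.** The point holds as a gap in a stated procedure. Clients are told that they may hide a refusal in a way that can leave a valid signature beside meaningless answers, and the available text does not keep that record out of the enrolment count, the intent-to-treat set or the medical-record request.

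Its statistical size is probably small: about 1 point of power at the pilot's open-refusal share, about 3 at an assumed 5% and about 7 at an assumed 10%. These figures rest on assumed shares, alpha and ICC, and on answers unrelated to condition. They describe added noise and a diluted effect, not a demonstrated bias.

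Three stronger readings go beyond the documents. They give no basis for refusal that differs by condition. They give no rate of covert refusal, so a figure such as 2% to 5% is illustration only. They also do not say that covert decliners will all skip follow-up; that is an inference. The use of data from people who meant to decline needs none of these and is reason enough for a small change.

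**What to change.** In Protocol 8.2 b and 8.2 d, replace the instruction to write random words with a private decline mark on the consent form, seen only by research staff. Decliners may still fill in the questionnaires as cover, so the privacy protection stays.

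State in the protocol and in SAP C.7 that a record with a marked, spoiled or unsigned consent is a non-enrolment:

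- the questionnaire is discarded;
- no medical record is requested;
- the person is not counted toward the 900 and is not in the intent-to-treat set.

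Make the decision from the consent form alone, before any follow-up data are seen, and report the counts by site and Step.

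The cost is a small form change, a few sentences of text and possibly a slightly lower enrolled count. It needs no extra visits or staff.
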